1.0 Investigational Design

1.1.Study Design

This investigation is a randomized controlled trial of three techniques to evaluate clinically, radiographic, and histologically the efficacy of L-PRF with freeze-dried bone allograft (FDBA) layered technique in improving quantity and quality of new vital bone formation and alveolar ridge dimensional stability following ridge preservation in comparison to L-PRF alone and L-PRF/FDBA.

Control technique: Ridge preservation using L-PRF/FDBA and ridge preservation using L-PRF alone

Test technique: Ridge preservation using L-PRF/FDBA layered technique

1.2. Objectives:

- To evaluate clinical and radiographic dimensional changes at alveolar ridge 3 months after ridge preservation procedure using L-PRF alone, L-PRF/FDBA, and L-PRF/FDBA Layered technique.

- To evaluate quantity and quality of new vital bone in sockets 3 months after ridge preservation procedure using L-PRF alone, L-PRF/FDBA, and L-PRF/FDBA Layered technique.

1.3. Hypotheses and Specific Aims:

- **Hypothesis 1:** Ridge preservation using L-PRF/FDBA Layered technique will best preserve alveolar ridge dimensions in comparison to using L-PRF alone.
- **Hypothesis 2:** Ridge preservation using L-PRF/FDBA Layered technique will improve new vital bone formation at the middle and apical thirds of the socket in comparison to using L-PRF/FDBA.

• Specific Aims:

1. To compare quantitative clinical alveolar ridge dimensions (in mm) 3 months after ridge preservation between the three groups using an intraoral scan and direct clinical assessment.

- 2. To compare quantitative two- and three- dimensional radiographic alveolar ridge dimensional changes (in mm) 3 months after ridge preservation between the three groups using Cone Beam Computed Tomography (CBCT) and virtual implant planning software.
- 3. To compare qualitative and quantitative histologic characteristics of new bone between the three groups after 3 months of ridge preservation by quantifying the distribution (in %) of new vital bone, connective tissue, residual graft particles, and artifact at the healed socket site.

2.0. Study Population

2.1 Entrance Criteria

Patients presented to the postdoctoral periodontal clinic at UAB School of Dentistry with a treatment plan for tooth extraction and implant placement will be screened according to the criteria. Thirty healthy adult eligible patients (ten in each group) of any ethnicity or gender may be enrolled into the study.

Participants must be at least 18 years old with demonstrated ability to understand and consent to the proposed study procedures. Decisionally-impaired adults and/or minors who cannot consent for themselves will not be enrolled.

Smokers (>10 cigarettes/day) patients or women who report a current pregnancy or patients who are not systemically healthy enough to receive out-patient elective dental care at the time of enrollment will be excluded.

Participants must have one or more hopeless single-rooted tooth that require extraction and planned to be replaced with a dental implant, with healthy adjacent teeth not planned for extraction. The extraction socket should have residual 4 bone walls following atraumatic tooth extraction.

Patients must demonstrate high compliance, adequate oral hygiene, and denied history of alcohol or drug abuse.

3.0 Study procedures

3.1 Summary of study procedures

• Screening/baseline visit: Upon enrollment into the study the patient's medical history and electronic records will be reviewed. Patients will be treatment planned by an interdisciplinary team consisting of a surgeon and a prosthodontist or restorative dentist. Clinical examiners will conduct clinical and radiographic exams to determine eligibility according to the above inclusion criteria. An intraoral scan will be taken to perform clinical measurements. Study visits and objectives will be explained to all participants. IRB approved written informed consent will be obtained from all the participants.

• Visit 1 (Surgical visit): Extraction and ridge preservation

• **Randomization:** Participants will be stratified and randomized to one of three treatment groups: Table 1, by permuted block randomization approach to ensure same number of patients in each group, using computer-generated random number list.

Table 1. Groups of treatment	
------------------------------	--

Group	Treatment	Number of participants
Group 1	Atraumatic tooth extraction followed by ridge preservation using	10
	Leucocyte and Platelet Rich Fibrin (L-PRF) + Freeze-Dried Bone	
	Allograft (FDBA) Layered technique	
Group 2	Atraumatic tooth extraction followed by ridge preservation using	10
	Leucocyte and Platelet Rich Fibrin (L-PRF) + Freeze-Dried Bone	
	Allograft (FDBA)	
Group 3	Atraumatic tooth extraction followed by ridge preservation using L-	10
	PRF	

• **Surgical procedure:** A loading dose of prophylactic antibiotic will be dispensed (Amoxicillin 2 grs or Clindamycin 600mg, 30 minutes to one hour prior to the surgery). Venous blood will be drawn (antecubital fossa) with a 25-butterfly needle to fill 4-8 collection tubes of 10ml each. The tubes will not contain any additive or anticoagulant. One tube will be centrifuged for 3 minutes and the other tubes will be centrifuged for 12 minutes. After centrifugation, L-PRF clots will be collected and stored in a closed sterile storage container that enables compression of clots into membranes/plugs. Additionally, the one tube that received less centrifugation (fibrinogen) will be used as an additive with the L-PRF membranes and bone allograft. The bone graft material utilized for patients in group 2 and 3 will be MinerOss cortico-cancellous freeze-dried bone allograft (FDBA).

L-PRF Preparation			
Venous blood collection	Centrifuge white-covered tube for 3 minutes and red- covered tubes for 12 minutes	White-covered tubes: Fibrinogen Red-covered tubes: L-PRF membranes	

After preparation and isolation of the surgical area, local anesthesia will be accomplished by infiltration and/or intraoral nerve block. Intravenous moderate conscious sedation or inhalation sedation will be used in patients who requested it.

Tooth or teeth will be gently elevated using a minimally traumatic technique that prevent loss of supporting bone. Socket(s) will be curetted, irrigated with saline, and inspected following extraction and verified for the presence of intact walls.

A Cone Beam Computed Tomography (CBCT) scan will be taken immediately after the tooth extraction, before ridge preservation procedure. It will serve for baseline radiographic measurements.

Group 1: L-PRF/FDBA Layered technique:

After socket is cleaned, a L-PRF plug will be formed, placed and compacted at the apical and middle third of the socket. Two membranes of L-PRF will be cut into small pieces and combined with 0.5 cc of cortico-cancellous bone allograft (FDBA), in a 50%-50% proportion, and fibrinogen forming sticky bone. The sticky bone will be placed and compacted at the coronal third of the socket (over the L-PRF plug already placed). A membrane of L-PRF will be placed at the coronal extent of the socket, flaps will be reapproximated and sutured with Monocryl 5-0 sutures.

Group 1: L-PRF/FDBA Layered technique	
	LPRF membranes

	L-PRF plug formed and placed in the apical and middle third of the socket
	L-PRF membrane chopped into small pieces and combined with FDBA and fibrinogen forming sticky bone
	Sticky bone is placed at the coronal third of the socket (over the L-PRF plug)

Group 2: L-PRF/FDBA:

After socket is cleaned, L-PRF membranes will be chopped into small pieces and combined with 0.5 cc of cortico-cancellous bone allograft (FDBA) and fibrinogen forming sticky bone. The sticky bone will be placed and compacted at the along the socket. A membrane of L-PRF will be placed at the coronal extent of the socket, flaps will be reapproximated and sutured with Monocryl 5-0 sutures.

Group 3: L-PRF

After the socket is cleaned, the socket will be completely filled with L-PRF plugs and a L-PRF membrane will be placed at the coronal extent of the socket, flaps will be reapproximated and sutured with Monocryl 5-0 sutures.

Post-surgical analgesics will be prescribed and/or dispensed as deemed necessary by the treating surgeon and a continued course of antibiotic will be prescribed for a 1-day time of period. Written and oral home care instructions will be provided.

- Visit 2 (Follow-up visit): Sutures will be removed after two weeks. Surgical site will be evaluated for healing status and post-operative instructions on resuming oral hygiene measures will be given to patients. Medical history will be reviewed, and patients will complete a questionnaire regarding their assessment of the post-operative discomfort they experienced during the initial healing phase, including number of days of altered activity/discomfort and number of tablets of pain medications taken.
- Visit 3 (Follow-up visit): After four weeks, surgical site will be evaluated for healing status and oral hygiene instructions will be reinforced. Medical history will be reviewed, and adverse events will be record.

• Visit 4 (Surgical visit): Bone biopsy and implant placement

After three months, surgical site will be evaluated. A second intraoral scan will be taken to evaluate clinical ridge dimensions. A second CBCT scan will be taken to evaluate the dimensional changes of the healed socket and plan the optimal implant location using implant planning software. Medical history will be reviewed, and adverse events will be record.

A surgical approach will be performed to take a bone biopsy for research purposes and implant placement at the same site. The procedure will be performed under local anesthesia and IV conscious sedation if patient requested it. After a full-thickness mucoperiosteal flap will be raised, the ridge dimensions will be measured at the crestal bone for dimensional changes in height and width using a calibrated surgical caliper and UNC-15 periodontal probe. Prior to implant placement, a bone biopsy will be taken from the center of the new bone using a 2mm internal diameter trephine bur. The dimensions of the harvested bone core will be 2mm in diameter and the length will be according to the implant dimension to be placed. The biopsy will be stored in 10% neutral buffered formalin and will be sent to the Histomorphometry and Molecular Analysis Core in the UAB Lyons Harrison Building. The Implant preparation osteotomy site will be completed following manufacturer protocol.

- Visit 5 (Follow-up visit): Sutures will be removed two weeks after the bone biopsy and implant placement. Surgical site will be evaluated for healing status and post-operative instructions on resuming oral hygiene measures will be given to patients. Medical history will be reviewed and patients will complete a questionnaire regarding their assessment of the post-operative discomfort they experience during the initial healing phase, including number of days of altered activity/discomfort and number of tablets of pain medications taken.
- Visit 6 (Follow-up visit): After four weeks, surgical site will be evaluated for healing status and oral hygiene instructions will be reinforced. Medical history will be reviewed, and adverse events will be record.
- Visit 7 (Final study visit): In six months, surgical site will be evaluated for healing status. This evaluation will include a clinical examination, periapical radiograph, intraoral scan, and assessment of overall oral health and hygiene. Patients will complete a questionnaire regarding their satisfaction with study participation. Patients will be offered a dental cleaning at no charge at this visit. Medical history will be reviewed, and adverse events will be record.

Table 2. Study schedule of events

Procedure Events	Screening	V1	V2 - V3	V4	V5-V6	V7
	Baseline	Extraction	2-4 wks	3 months	2-4 wks	6
		& ridge	Follow-	Bone biopsy	Follow-	months
		preservation	up	and implant	up	
		-	-	placement	-	
IRB-Consent	Х					
Medical history	Х	Х	Х	Х	Х	Х
review						
Inclusion/exclusion	Х					
criteria						
Oral exam	X	X	Х	X	Х	Х
Randomization to		Х				
either group						
Tooth		Х				
extraction/Ridge						
preservation						
Bone core biopsy				X		
Implant placement				X		
X-ray	X			Х		Х
CBCT		X		X		
Intraoral Scan	Х			Х		Х
Photograph	Х	Х	Х	Х	Х	Х
Clinical	Х	Х		Х		
assessment of ridge						
dimensions						
Radiographic		Х		Х		
assessment of ridge						
dimensions						
Histologic				Х		
evaluation						
Adverse events			Х		Х	Х
recorded						
Pt. satisfaction						Х
survey						
Statistical						Х
Analysis/Final						
Report						

3.2.Visual Analog Scale (VAS) survey is a questionnaire regarding post-operative pain, swelling, bruising effect, and daily activities tolerance. For each question, patients are asked to mark on a 0 to 10 scale their perception of the level of corresponding pain, swelling, bruising, and alterations to daily activities with 0 being no symptoms and 10 being the worst symptom imaginable. It will be completed two weeks after every surgical procedure.

3.3.Outcomes measurements:

• Clinical and Radiographic Measurements:

Clinical measurements will be taken by one experienced blinded examiner to the randomization process before ridge preservation procedure and 3 months after ridge preservation, using intraoral scan and direct clinical assessment using a calibrated surgical caliper and UNC-15 periodontal probe (in millimeters). Another blinded examiner will perform the radiographic measurements at time of ridge preservation procedure and 3 months after ridge preservation, using a CBCT and implant planning software (in millimeters). Horizontal and vertical ridge dimensions will be evaluated clinically and radiographic. Intra-examiner calibration will be conducted to ensure reliability of measuring method.

• Histomorphometric Analysis:

Each specimen will be fixated with 10% neutral buffered formalin for 48 hours prior to be dehydrated and embedded in methylmethacrylate. It will be ground sectioned at the center of the biopsy in its long axis into 50-70 micron-thick sections (Exakt Technologies, Inc., Oklahoma City, OK), and polished with 4000 grit sandpaper and Novus Polish to create a surface as smooth as possible. All sections will be stained with Sanderson's Bone Stain and imaged for quantification of bone formation. Histomorphometry will be done using the Bioquant Image Analysis Software (R&M Biometrics, Nashville, TN) by measuring the total surface of vital bone, residual graft particles, organic matrix and artifact/air components. Corresponding percentages will be calculated for each of these tissues and compared between the three groups (L-PRF, L-PRF/FDBA, LPRF/FDBA layered technique). These experiments and measurements will be conducted by an experienced blinded lab technician.

3.4.Statistical Analysis:

A power analysis was conducted to determine the sufficient number of patients in each treatment group to obtain a power of 80% to detect a 1.0mm change in ridge dimensions using a type 1 (alpha) error rate of 0.05. The power analysis determined that a minimum of 10 patients would be required for each group, and 30 patients in total. An alpha of 0.05 was assumed after a Bonferroni correction for five relevant 2-way comparisons between the treatment groups.

Two-tailed *t* test will be used to compare clinical characteristics between patients with the L-PRF/FDBA layered technique, L-PRF/FDBA, and those with L-PRF alone for continuous variables with a normal distribution. Nonparametric (Wilcoxon) test will be used otherwise.

For categorical variables, inter-group comparisons will be conducted using chi-square test or Fisher's Extract Test, as deemed necessary. To determine whether the groups experienced equivalent changes in bone growth from baseline to follow-up, paired *t* (or Wilcoxon signed-rank) and Mc Nemar's tests will be used for continuous and categorical variables, respectively.

The α level will be set at 0.05. Statistical analysis will be carried out using SAS software version 9.4 (SAS Institute, Inc, Cary, North Carolina).

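### The intraoral-scan ridge change compares a tooth-bearing Screening surface with a healed ridge, and the direct caliper baseline at Visit 1 is scheduled but not defined

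*Combined protocol and SAP*

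**What the plan says.** **Scan.** Section 2.1 enrols patients whose tooth still has to come out: "Participants must have one or more hopeless single-rooted tooth that require extraction". At the Screening visit (section 3.1), "An intraoral scan will be taken to perform clinical measurements". Extraction follows at Visit 1. At Visit 4, three months later, "A second intraoral scan will be taken to evaluate clinical ridge dimensions". Table 2 marks scans at Screening, Visit 4 and Visit 7, and none at Visit 1.

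**Caliper and probe.** At Visit 4 the direct reading is on bone: "After a full-thickness mucoperiosteal flap will be raised, the ridge dimensions will be measured at the crestal bone for dimensional changes in height and width". Table 2 marks the clinical ridge assessment at Screening, Visit 1 and Visit 4. The Visit 1 surgical steps mention no caliper or probe. They do say, for each of the three groups, that flaps are closed at the end.

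**Outcome definition.** Section 3.3 times the clinical measurements "before ridge preservation procedure and 3 months after ridge preservation, using intraoral scan and direct clinical assessment using a calibrated surgical caliper" and a periodontal probe, and says that horizontal and vertical ridge dimensions are assessed both clinically and radiographically.

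**CBCT.** The first CBCT is taken after extraction and before grafting, and "It will serve for baseline radiographic measurements".

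**Analysis.** Section 3.4 applies paired tests to baseline-to-follow-up change in bone growth. The sample size is set "to detect a 1.0mm change in ridge dimensions", with no instrument, axis or SD named.

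**The concern.** A change score can be interpreted only if both readings are of the same structure in the same tissue state. The CBCT meets that condition: bone after extraction at Visit 1 against bone at Visit 4. The scan does not. It records surfaces, so at Screening it shows crown and gingiva, and at Visit 4 it shows mucosa over a healed edentulous ridge. No edentulous crest exists at Screening from which to measure height.

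For the caliper and probe, the plan fixes the tissue state at Visit 4 but not at baseline. An examiner following it could take the Visit 1 reading before or after extraction, and over mucosa or on bone.

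At stake is the clinical half of the first objective in section 1.2, which concerns clinical as well as radiographic dimensional change. The within-arm paired tests are most exposed, because nothing in them removes a shift shared by all patients.

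**Working it through.** **1. What each instrument compares**

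| Instrument | Baseline | 3 months (Visit 4) | Like for like? |
|---|---|---|---|
| Intraoral scan | Screening, tooth present, surface only | Healed ridge, surface only | No |
| Caliper/probe | Ticks at Screening and Visit 1; method not described | Crestal bone, flap raised | Cannot be determined |
| CBCT | Visit 1, after extraction, before grafting | Second CBCT, healed socket | Yes |

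**2. What enters the change score**

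Let B be bone width and M soft-tissue thickness, with subscript 0 for baseline and 3 for three months.

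- Scan width, at a level below the gingival margin: (B3 + M3) − (B0 + M0) = change in B + change in M.
- Scan height: the baseline surface is tooth and gingival margin, so the change also contains the loss of the crown.
- Direct reading, bone against bone: B3 − B0 = change in B.
- Direct reading, if the baseline were taken over mucosa: B3 − (B0 + M0) = change in B − M0.

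Only the third expression is bone change.

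**3. Within arms and between arms**

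A paired test within an arm carries the full mean of the extra term. In a randomized comparison, baseline quantities such as M0 and the crown have the same expected value in each arm, so their means largely cancel and their patient-to-patient variance remains. A between-arm bias would need an extra term that depends on technique, for example M3 differing by graft. The documents give no information on that.

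**4. The plan's own figure, and what extra noise could do**

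The stated size is 10 per group for 80% power and 1.0 mm. With no SD given, it cannot be reproduced, only solved backwards. For a two-sided two-sample t test with 18 degrees of freedom, the noncentrality is 1.0 / (SD × √(2/10)). Power of 80% at alpha 0.05 requires SD = 0.755 mm, since 1.0 / (0.755 × 0.447) = 2.96. The normal approximation gives 0.798 mm. If alpha is 0.05/5 = 0.01, reflecting the five comparisons in section 3.4, the values are 0.593 and 0.654 mm.

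Add independent noise with SD s, so that the new SD = √(0.755² + s²). For example, √(0.570 + 0.250) = 0.905. At alpha 0.05:

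| Assumed s (mm) | SD (mm) | Power, 10 per group | n per group for 80% |
|---|---|---|---|
| 0 | 0.755 | 80% | 10 |
| 0.25 | 0.795 | 76% | 11 |
| 0.50 | 0.905 | 65% | 14 |
| 0.75 | 1.064 | 51% | 19 |
| 1.00 | 1.253 | 39% | 26 |

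Every s here is an assumption. The table shows sensitivity only. It would apply only if the 1.0 mm target were tested on a mismatched clinical measure, and the plan does not say which measure the target refers to.

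**The case against.** The strongest reply is that Table 2 has a coherent reading. The scan is the only clinical-measurement instrument named for Screening, so the Screening tick is the scan and the Visit 1 tick is the direct reading: one baseline per instrument. Flap closure at Visit 1 implies some flap elevation, so bone may have been accessible. Section 3.3 separates clinical from radiographic measurement and gives each its own blinded examiner, and section 1.3 gives them separate aims. Aim 1 speaks of dimensions at 3 months, which could be met from Visit 4 values alone. Retained adjacent teeth could serve as scan references.

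Most of this stands, and it limits the point. A reader might infer that the plan sets an over-mucosa Screening caliper reading against bare bone at Visit 4. With an assumed 1.0 to 1.5 mm of mucosa per side, that would create 2 to 3 mm of false width loss, two to three times the 1.0 mm target. The documents do not support that inference: no section describes a Screening caliper reading, none makes that pairing, and a Visit 1 assessment is scheduled.

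Two things survive. The coherent reading does not help the scan, whose only baseline still precedes extraction; adjacent teeth fix the position of the surface but do not turn it into bone. And the Visit 1 direct reading still has no stated tissue state, landmark or timing relative to extraction. The Aim 1 wording does not remove the need for a baseline, because the Visit 4 direct reading is itself taken to assess change, and section 1.2 asks for clinical change.

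**Conclusion.** The point holds in two parts of different strength.

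- **Scan: established from the text.** As scheduled, scan change is a change in surface from a tooth-bearing site to a healed ridge. It is not bone change and should not enter the paired tests of bone growth. Height is the worst affected.
- **Caliper and probe: under-specified.** The plan allows a mismatched baseline but does not require one.

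The main consequence is a within-arm change that cannot be read as bone change. Between arms, the expected effect is added noise of unknown size. A reader might infer that the arm comparison in Hypothesis 1 is biased; that would need a soft-tissue effect differing by technique, which the documents neither state nor rule out. No power loss can be attributed to the plan, since the SD, the noise and the measure behind the 1.0 mm target are all unstated. CBCT and histology are unaffected. Which measurement the 1.0 mm target refers to is a separate matter of endpoint definition.

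**What to change.** **(a) Scan.** In sections 3.3 and 3.4, state that scan change is analysed and reported only as soft-tissue contour change, at fixed levels referenced to the retained adjacent teeth. Exclude it from the bone-change tests, never pair or pool it with caliper or CBCT values, and do not report scan height as ridge-height change.

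**(b) Direct reading.** In the Visit 1 steps, describe the caliper and probe reading that Table 2 already schedules: after extraction, before grafting, at the same crestal-bone landmark as Visit 4. Make it the only baseline for the direct measurement, and add a note to Table 2 that the Screening tick refers to the scan alone.

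**Cost.** Protocol wording, a table note and a short landmark-matched reading at a surgery already planned. Scan-based height is given up as a ridge outcome. The extent of the Visit 1 flap is not described, so the surgical team should confirm that the landmark can be reached within the exposure already planned. The wording should be settled before the surgeries, because a pre-graft reading that is missed cannot be recovered.

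### Randomisation is described as stratified, but no factor is named and the between-group tests ignore the strata; if the factor is prognostic, those tests are conservative and give up power that an adjusted analysis would keep

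*Combined protocol and SAP*

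**What the plan says.** The Randomization paragraph of section 3.1 reads "Participants will be stratified and randomized to one of three treatment groups", and continues "by permuted block randomization approach to ensure same number of patients in each group, using computer-generated random number list". Table 1 gives 10 participants per group. The document does not give a stratification factor, a number of strata or a block size.

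Section 3.4 (Statistical Analysis) sets out the tests:

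- Continuous variables between groups: "Two-tailed *t* test will be used to compare clinical characteristics between patients with the L-PRF/FDBA layered technique, L-PRF/FDBA, and those with L-PRF alone".
- Non-normal variables: "Nonparametric (Wilcoxon) test will be used otherwise".
- Categorical variables: "For categorical variables, inter-group comparisons will be conducted using chi-square test", or Fisher's exact test.
- Change from baseline: paired t, signed-rank and McNemar tests, introduced by "To determine whether the groups experienced equivalent changes in bone growth from baseline to follow-up, paired".

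None of these has a stratum term. No covariate model or stratified test is named.

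**The concern.** Taken literally, sections 3.1 and 3.4 do not fit together. Stratified allocation balances the factor across arms, so variation between strata drops out of the difference between two arm means. The two-sample t test still counts that variation in its standard error. If the factor is related to outcome, the standard error is too large for the design, p values tend to be too high, and the true type I error lies below the nominal level.

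What is at stake is precision that the randomisation would already have provided, in a trial with 10 patients per arm. There is also a question of prespecification: if the plan is silent, the choice between an adjusted and an unadjusted result could be made after the data are seen.

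**Working it through.** **The plan's own figure.** Section 3.4 gives 80% power, a 1.0 mm difference, alpha 0.05 and 10 patients per group, but no SD. The 10 therefore cannot be reproduced, only inverted. For a two-sided t test with 10 per arm (18 df), the power is 80% when the SD is 0.755 mm, a standardised difference of 1.0/0.755 = 1.325. The normal approximation gives 0.798 mm. The 0.755 mm is an assumption used to set the scale. The power comparison below depends only on the standardised difference.

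**Set-up (assumed).** Two equal strata, 5 patients per arm in each. The stratum explains a share R² of the outcome variance σ², and there is no treatment-by-stratum interaction.

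**Standard error.**

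- True variance of the difference between two arm means, with strata balanced: 2σ²(1 − R²)/10.
- The t test's average estimate of it: 2σ²(1 + R²/9)/10. The 1/9 arises because a balanced stratum contributes R²σ² × 10/9 to the within-arm sample variance: (1 − R²) + 10R²/9 = 1 + R²/9.
- Ratio of estimated to true variance: (1 + R²/9)/(1 − R²).

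This ratio is 1.00 at R² = 0. At R² = 0.1 it is 1.0111/0.9 = 1.12, at 0.2 it is 1.0222/0.8 = 1.28, and at 0.3 it is 1.0333/0.7 = 1.48. The square roots show the standard error to be too large by about 6%, 13% and 22%.

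**Type I error and power.** Simulation of the same two-arm comparison, 100,000 trials per setting, two-sided alpha 0.05. The plain t test has 18 df. The model with a stratum term has 20 − 2 − 1 = 17 df.

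| R² | Type I error, t test | Power, t test | Power, stratum term |
|---|---|---|---|
| 0 | 4.9% | 80.0% | 79.7% |
| 0.1 | 3.9% | 80.8% | 83.8% |
| 0.2 | 2.9% | 81.7% | 87.6% |
| 0.3 | 2.0% | 82.8% | 91.6% |
| 0.5 | 0.5% | 86.0% | 97.7% |

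The adjusted test stays at about 5% type I error throughout. Its power can be checked exactly from a noncentral t with 17 df and noncentrality 1.325/√(0.2(1 − R²)). This gives 79.7%, 83.7%, 87.7%, 91.5% and 97.6%, in agreement with the last column.

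**Pooling three arms.** One model over all 30 patients has 30 − 3 − 1 = 26 error df. The same formula with 26 df gives 81.4%, 85.2%, 89.0% and 92.6% for R² of 0, 0.1, 0.2 and 0.3, which is 1.7, 1.5, 1.3 and 1.1 points above the 17 df values. This part of the gain comes from pooling, not from the stratum, and it assumes a common variance in the three arms.

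**A stricter alpha.** The Bonferroni sentence in section 3.4 can also be read as 0.05/5 = 0.01 per comparison. The back-solved SD is then 0.593 mm. Power is 80.0% unadjusted against 79.4% adjusted at R² = 0, and 82.3% against 93.1% at R² = 0.3. The pattern is the same.

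**The case against.** The strongest objection is that the trial may not be stratified at all. The sentence gives equal group sizes as its purpose and refers to a single computer-generated list, which describes plain blocking. Separate lists per stratum guarantee 10 per arm only if every stratum fills complete blocks. With blocks of three, strata of 15 and 15 do so (five blocks each), but strata of 14 and 16 do not. This objection stands as a possibility that only the sponsor can settle. If it is right, the remedy is to delete one word and the tests in section 3.4 need no stratum term.

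A second objection is that the loss is conditional. Without a named factor, nothing shows that it predicts ridge dimensions or bone histology, and at R² = 0 the loss vanishes. This also stands, so the size can be given only as a range. It does not remove the case for adjusting: the cost is about 0.3 points of power if the factor is irrelevant, against a gain of about 3 to 9 points at R² of 0.1 to 0.3.

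Some stronger readings are tempting but not supported:

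- *The omission leaves the trial short of its planned power.* In every setting the plain t test stays at about 80% or above. The shortfall is only against an adjusted analysis that the plan did not promise.
- *The false-positive rate is inflated.* The error goes the other way.
- *Every analysis is affected.* The argument concerns the error term of the between-arm contrast. It does not reach the paired t, signed-rank and McNemar tests of change within a group.
- *Confidence intervals will be reported with the wrong coverage.* Section 3.4 plans no intervals. Any built on the same standard error would be too wide, not too narrow.

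**Conclusion.** The point holds in conditional form. Sections 3.1 and 3.4 are inconsistent as written: allocation is called stratified, the factor is undefined, and the between-group tests ignore it. If the factor is prognostic, the t test is conservative. True type I error is about 4%, 3% or 2% instead of 5% when the stratum explains 10%, 20% or 30% of the variance, and power is about 3, 6 or 9 points lower than in a like-for-like adjusted comparison. If the factor is not prognostic, or there is no stratification, nothing is lost.

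The direction is firm for any prognostic factor balanced by design. The size rests on assumed variance shares, two equal strata and an SD back-solved from the stated power. The figures are for the t test only; the corresponding loss for the Wilcoxon and categorical tests was not calculated.

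**What to change.** In section 3.1, state the factor used to stratify. With 30 patients in three arms, keep it to one factor with few levels.

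In section 3.4, take the between-group comparisons of continuous outcomes from one linear model over all three arms, with treatment and the stratification factor as terms, and report pairwise contrasts. Where a Wilcoxon rank-sum test was planned, use the van Elteren test stratified by the same factor. State that the three-arm model assumes a common variance. Leave the within-group paired tests as they are as far as this point is concerned.

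If allocation is in fact only blocked, delete 'stratified' from section 3.1. The stratum term is then not needed.

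The cost is wording, plus one degree of freedom for a two-level factor: about 0.1 to 0.3 points of power at alpha 0.05 if the factor is not prognostic, and about 0.6 points (80.0% against 79.4%) at alpha 0.01. The change should be made before any outcome data are compared by arm.
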